9.3.1. Summary of sample size

Although the maximum sample size from the above calculations is a total of 121 patients (65 in the NexoBrid group, 13 in the Gel vehicle group and 43 in the SOC group (to match NexoBrid numbers)), we propose entering larger numbers to provide an extra margin of assurance in achieving positive results on the efficacy outcomes, and adequate information on safety outcomes to allow better benefit vs. risk assessment.

Therefore, we plan a study with total sample size of 175 patients; 75 (NexoBrid) + 75 (SOC) + 25 (Gel Vehicle).

9.4. Safety Set

The safety set includes all patients who received a treatment and analysis is focused on the treatment actually performed.

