7.1.4. Drop-out criteria

After screening and prior to treatment any changes in the patient's medical condition should be assessed. The patient should be excluded from treatment if these changes represent deterioration in his/her condition which may affect the patient's safety and/or suitability for the study (e.g. exclusion criteria).

Throughout the course of a subject's participation in the study, he/she may be removed from the study as follows:

- Whenever it is necessary to safeguard his/her welfare as judged by the Principle Investigator,
- Participation in another investigational drug trial,
- Subjects who express a desire to withdraw from the study,
- Subjects with EAR identified post randomization but prior to treatment.

The reason for any subject withdrawal from the study should be recorded in the eCRFs and the occurrence should be reported to the sponsor. Early termination visit should include final assessments as in the Hospital Discharge visit, as applicable (please refer to Section 8.7 of the study protocol).

Discontinued subjects will not be replaced.

When a subject is removed from the study treatment, he/she will receive treatment according to the standard of care as appropriate in the investigative site and will be followed up according to the study schedule, in accordance with patient's availability.

7.1.4.1. *Stopping rules (apply for NexoBrid or Gel Vehicle arms only)*

Treatment (eschar removal) should be stopped following a safety concerns raised by the treating physician or if a patient expresses his desire to withdraw from the study. In addition, in the following situations:

Burn Induced Compartment Syndrome (BICS) Monitoring and Diagnosis

All circumferential wounds should be closely monitored during treatment for signs of improvement or deterioration that may require escharotomy. If clinical assessment and SpO₂ monitoring are possible, they will be done continuously and recorded in the eCRFs every 2 hours. If such assessment is not practical, direct pressure will be measured every 2 hours from start of the eschar removal. The eschar removal process shall be discontinued (escharotomy may be performed at the discretion of the physician in any of the following cases:

- Increasing interstitial/compartment pressure >30 mmHg
- Difference of >20 mmHg of diastolic pressure between the opposite uninjured extremity

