10.2. Handling of Withdrawals and Dropouts

Withdrawn subjects will be evaluated in the FAS and safety set. Missing values are imputed as mentioned in Section 10.1.

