11.1.4. Safety variables

All safety variables except for the first safety endpoint "time to wound closure" will be evaluated on the safety set.

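### The SAP contradicts itself on which population carries the NexoBrid versus SOC safety comparison, and its safety-set rule, read literally, counts topical-arm patients removed before any application under SOC

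*SAP*

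**What the plan says.** Five places in the SAP bear on this point.

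- **Section 7.1.4 (Drop-out criteria).** One listed ground for removal is "Subjects with EAR identified post randomization but prior to treatment" (EAR means extremities at risk). Separately, changes found between screening and treatment are to be assessed: "The patient should be excluded from treatment if these changes represent deterioration in his/her condition". The section then says: "When a subject is removed from the study treatment, he/she will receive treatment according to the standard of care as appropriate", and such a subject "will be followed up according to the study schedule", subject to availability.
- **Section 10.2.** "Withdrawn subjects will be evaluated in the FAS and safety set".
- **Section 9.4.** "The safety set includes all patients who received a treatment and analysis is focused on the treatment actually performed". The SAP does not define what counts as a treatment here.
- **Section 11.1.4.** "All safety variables except for the first safety endpoint 'time to wound closure' will be evaluated on the safety set". Section 11.1.4.1 puts time to wound closure on the FAS.
- **Sections 9.5 and 9.6.** The FAS is all randomised patients, analysed by planned treatment. Section 9.6 names the FAS as the source not only of the efficacy analyses but also of the comparative safety analyses.

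Two further places matter. Section 7.1.1.2 describes the SOC arm as surgical and/or non-surgical eschar removal chosen by the burn specialist, so site standard of care cannot be told apart from SOC-arm treatment. Section 10.3.5.3 counts topical applications as 0, 1 or 2, so topical-arm patients with no application are foreseen.

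**The concern.** An as-treated safety set is conventional. In this trial, though, the care given to a patient taken off study treatment is also the comparator. A topical-randomised patient who develops EAR, or is found after randomisation to have deteriorated, and who never receives the gel is then treated with standard of care. Under 9.4, taken literally, that patient is analysed as SOC. An SOC-randomised patient with the same problem also stays in SOC. The SOC column would hold the pre-treatment removals of all three arms, and the NexoBrid column would hold none.

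Objective 3 in Section 2.2 is safety compared with SOC. If removed patients do worse than the rest, then adverse events, SAEs, transfusions, antibiotic use and readmissions look worse under SOC with no drug effect at all. Whether this reaches the comparison depends on whether the programmer follows 11.1.4 or 9.6, and the SAP does not settle that.

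**Working it through.** **Text check.** The steps are removal before treatment (7.1.4), standard of care and follow-up (7.1.4), retention in the safety set (10.2), grouping by treatment performed (9.4), and use of that set for the safety variables (11.1.4). No section states the resulting move to the SOC column. It is the literal consequence of reading these together. Section 9.6 leads to the opposite grouping for comparative safety.

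**Size.** The SAP states no figure on this point, so there is none to reproduce. The only inputs it supplies are the planned arm sizes in 9.3.1: 75 NexoBrid, 75 SOC, 25 Gel. The rest is assumed:

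- *q*: share of each arm removed before treatment (the same in all arms);
- *R*: SAE risk in removed patients;
- *r*: SAE risk in all others, with no treatment effect.

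By treatment performed, NexoBrid has risk *r*. SOC has 75 + 100*q* patients, of whom 75*q* + 100*q* = 175*q* are removed cases. So:

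SOC rate = [*R* × 175*q* + *r* × 75(1 − *q*)] / (75 + 100*q*)

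False difference = 175*q*(*R* − *r*) / (75 + 100*q*)

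By randomised arm, both rates are (1 − *q*)*r* + *qR* and the difference is zero.

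| Assumed *q*, *R*, *r* | SOC as treated | NexoBrid as treated | False difference | Both arms as randomised |
|---|---|---|---|---|
| 2%, 30%, 10% | (0.3 × 3.5 + 0.1 × 73.5)/77 = 10.9% | 10.0% | 0.9 points | 10.4% |
| 5%, 50%, 10% | (0.5 × 8.75 + 0.1 × 71.25)/80 = 14.4% | 10.0% | 4.4 points | 12.0% |
| 8%, 50%, 10% | (0.5 × 14 + 0.1 × 69)/83 = 16.7% | 10.0% | 6.7 points | 13.2% |

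A second set of assumptions, with a background event rate of 20%, gives the same direction: 0.5 points at *q* = 1%, *R* = 40%, and 6.2 points at *q* = 4%, *R* = 90%. The difference is zero whenever *R* = *r*.

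**Would keeping these patients out of the SOC column be enough?** In the central case SOC then has its own 75 patients: (0.5 × 3.75 + 0.1 × 71.25)/75 = 12.0%, against 10.0% for NexoBrid. A difference of *q*(*R* − *r*) = 2.0 points remains, because NexoBrid has still lost its own removed patients. Only grouping by randomised arm brings it to zero.

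**The case against.** The strongest reply is Section 9.6. If the comparative safety analyses come from the FAS by planned treatment, the bias does not arise and tables by randomised arm are already promised. That is correct as far as it goes, but 11.1.4 says otherwise for every safety variable but one. The two sections conflict, and 9.6 does not resolve it.

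Second, 7.1.4 generally uses the word treatment for study treatment. If 9.4 means the same, a topical-randomised patient removed beforehand falls outside the safety set and is not added to SOC. The wording allows this, but it sits badly with 10.2. It also still takes removed patients out of NexoBrid. If SOC-randomised removals remain as SOC-treated, the residual 2.0 points of the central case apply. Only if they too were dropped would the difference vanish.

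Third, the numbers are probably small. EAR is an exclusion criterion (7.1.3.3, no. 6) and is to be identified at screening (Table 1, footnote 11). The deterioration clause also covers the time before randomisation, so only part of it is relevant. This stands.

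Fourth, events with onset before treatment are tabulated separately (11.1.4.4), and transfusions are split in the same way (11.1.4.11). That isolates the early events. Later events in the same patients would still fall in the column to which those patients are assigned.

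A reader might infer that topical removals will be more frequent because the treating team knows the allocation. Nothing in the SAP shows this, and the argument does not need it.

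**Conclusion.** The point holds as a contradiction between 9.6 and 11.1.4, combined with a safety-set rule that, read literally, places never-applied topical patients under SOC. The direction favours NexoBrid if removed patients fare worse than the others. Time to wound closure is on the FAS and is unaffected.

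A reader might go further and conclude that the SAP moves these patients to SOC by a stated rule, or that the safety comparison is biased by 4.4 points. The documents support neither. The move is an inference from an undefined phrase, 9.6 points the other way, and every removal and SAE rate used above is an assumption. What can be said is that the false difference would be about 0.9 to 6.7 points over the assumed range, that about 2.0 points of the central 4.4 do not come from adding topical patients to SOC, and that the true number affected is not given.

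**What to change.** 1. Reconcile 9.6 and 11.1.4 so that the comparative AE and SAE tables, and the other comparative safety tables, are by randomised arm on the FAS. Give as-treated tables of patients exposed to each topical agent alongside.
2. In 9.4, define what counts as a treatment. State that topical-randomised patients with zero applications appear in their own row or listing, not in the SOC column.

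The second change alone is not enough, because it leaves the residual difference shown above. The cost is SAP wording and one extra table run. The one drawback is that denominators differ slightly between the two sets of tables, which a footnote can explain. No trial procedure changes.

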9.5. Full analysis Set (Intent-to-Treat population)

The full analysis set (FAS) includes all patients who are randomized into the trial. The analysis is focused on the planned treatment.

9.6. Per Protocol Set

The per protocol (PP) set includes all subjects who do not have major protocol violations (cf. section 8). Analysis of the PP population is for supportive purposes, whereas the analysis of the ITT population (FAS) provides the primary and secondary efficacy and the comparative safety analyses. The PP analysis will include patients in the treatment group according to treatment received.

9.7. Enrolled population

The enrolled population consists of all subjects who passed through the screening processes and signed informed consent.

10. Data Handling

10.1. Handling of Missing Data, Outliers and Implausible Data

Missing data in the primary and secondary outcomes is the main concern.

10.1.1. Primary Endpoint: Incidence of complete eschar removal

Little or no missing data are expected for the primary endpoint, since the outcome is assessed only several hours after the start of treatment for both NexoBrid and Gel Vehicle groups. The main analysis will be a complete-case analysis. In each treatment group, only patients with documented total eschar removal (at the end of the eschar removal soaking period) will be counted and this number divided by the total number of complete cases.

Three sensitivity analyses will be conducted for this endpoint. A first analysis will count all patients with missing data (for this endpoint) as positive (i.e. complete eschar removal) and a second analysis will count all patients with missing data as negative (i.e. no complete eschar removal). The third sensitivity analysis will be a tipping point analysis, in which the effect of missing data on the conclusion will be investigated. This analysis will be conducted as follows:

1. Impute the entries of the incomplete data sets $m = 100$ times from Bernoulli distributions. For the imputations of the Gel Vehicle group, the event probability p is chosen as the observed incidence of complete eschar removal in the Gel group (without missing data). For the NexoBrid group the event probability will be $p = p_{obs} - s$, where s is a shift parameter (see below). The random seeds for the imputations will be 14983,...,15082.
2. For each of the 100 imputed data sets compute Fishers exact test and calculate the proportion of tests that reject the null-hypothesis.
3. Repeat steps 1. and 2. for $s = 0, 0.05, \dots$ as long as $p_{obs} - s$ is still non-negative.

The analysis outlined here allows investigating for which assumed success probability for the patients with missing data in the NexoBrid group, the conclusion of the analysis remains stable.

Secondary Endpoints

10.1.1.1. Secondary Endpoint: Incidence of surgical excision

The same procedure as for the primary endpoint will be applied for this endpoint, i.e. the main analysis will be a complete-case analysis. In each treatment group, only patients with documented surgical excision will be counted and this number divided by the total number of randomized subjects with non-missing endpoint. Two sensitivity analyses will be conducted for this endpoint. A first analysis will count all patients with missing data (for this endpoint) as positive (i.e. no surgical excision performed) and a second analysis will count all patients with missing data as negative (i.e. surgical excision performed).

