9.2. Secondary Endpoint: Incidence of surgical excision

Estimated proportions having surgical excision from study MW2004-11-02: NexoBrid 0.22; SOC 0.62

Standard errors: NexoBrid 0.048; SOC 0.054

Difference = 0.40; Standard error of difference = 0.072

Anticipated difference: $0.40 - 0.072/2 \approx 0.36$

We therefore take the anticipated proportion with complete excision to be: NexoBrid 0.24 and SOC 0.60.

Using Fisher's exact test, the sample size needed to achieve 90% power using a two-sided significance level of 5% is **86**: 43 in the NexoBrid group and 43 in the SOC group.

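### For surgical excision, both planned missing-data runs fill the two arms alike, so the case unfavourable to NexoBrid is left untested

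*SAP*

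**What the plan says.** SAP section 10.1.1.1 opens by referring back to the primary endpoint's procedure, then narrows the reference: "i.e. the main analysis will be a complete-case analysis". It continues: "Two sensitivity analyses will be conducted for this endpoint". In the first, "A first analysis will count all patients with missing data (for this endpoint) as positive (i.e. no surgical excision performed"). In the second, "a second analysis will count all patients with missing data as negative (i.e. surgical excision performed").

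Section 10.1.1 gives the primary endpoint three sensitivity analyses. Two are uniform fills of the same kind. In addition, "The third sensitivity analysis will be a tipping point analysis, in which the effect of missing data on the conclusion will be investigated". That analysis lowers the imputed success probability in the NexoBrid arm alone and keeps the Gel Vehicle arm at its observed rate.

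Section 11.1.3.1 analyses excision by covariate-adjusted logistic regression and reports an odds ratio. It adds a per-protocol repeat and further covariate and wound-level models, but nothing that varies the missing-data assumption by arm. Section 11.1.8 places excision directly after the primary endpoint in the testing hierarchy.

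**The concern.** A sensitivity analysis for missing data should show how far the conclusion depends on what is assumed about unseen patients. For a superiority claim, the demanding assumption is that missing patients did badly on the test arm and well on the comparator. Filling both arms with the same outcome does not approach that assumption. With similar missingness it shifts both proportions by the same amount and leaves their difference unchanged. Two agreeing runs could then be read as evidence of robustness when the relevant departure was never examined.

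Excision gates the tests of time to complete eschar removal and blood loss. Some missing excision data are also plausible. The FAS contains all randomized patients (section 9.5), section 7.1.4 allows removal after randomization and before treatment, and section 10.1 names missing data in the primary and secondary outcomes as the main concern.

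**Working it through.** **Inputs from the SAP.** Anticipated excision rates, section 9.2: "We therefore take the anticipated proportion with complete excision to be: NexoBrid 0.24 and SOC 0.60". Planned arm sizes, section 9.3.1: 75 NexoBrid and 75 SOC. Two-sided level 5%.

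**The plan's own figure.** Section 9.2 gives 43 per arm for 90% power with Fisher's exact test. Exact enumeration at 43 per arm, 0.24 versus 0.60, gives power 0.904, so the stated size is reproduced.

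**Assumptions.** The SAP states no missing rate for excision, so a range of missing counts is used, equal in the two arms unless stated. P-values are unadjusted Fisher tests, not the planned adjusted model. Counts are rounded to whole patients.

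**Algebra.** Let m be the missing share in each arm, and pN and pS the observed excision rates.

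- All missing not excised: (1−m)pS − (1−m)pN = (1−m)(pS − pN).
- All missing excised: [(1−m)pS + m] − [(1−m)pN + m] = (1−m)(pS − pN).
- Arm-opposed (missing NexoBrid excised, missing SOC not excised): (1−m)pS − [(1−m)pN + m] = (1−m)(pS − pN) − m.

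The two planned runs coincide on the risk-difference scale, and the unfavourable case lies below both by m.

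**Design rates, 0.24 versus 0.60, 75 per arm (NexoBrid versus SOC excised)**

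| Missing per arm | All not excised | All excised | Arm-opposed |
|---|---|---|---|
| 5 | 17 vs 42: 33.3 points | 22 vs 47: 33.3 points | 22 vs 42: 26.7 points, p=0.0016 |
| 8 | 16 vs 40: 32.0 points, p=0.00009 | 24 vs 48: 32.0 points, p=0.00015 | 24 vs 40: 21.3 points, p=0.013 |
| 10 | 16 vs 39: 30.7 points | 26 vs 49: 30.7 points | 26 vs 39: 17.3 points, p=0.048 |
| 11 | 15 vs 38: 30.7 points, p=0.00015 | 26 vs 49: 30.7 points, p=0.0003 | 26 vs 38: 16.0 points, p=0.069 |
| 15 | 14 vs 36: 29.3 points, p=0.00024 | 29 vs 51: 29.3 points, p=0.00054 | 29 vs 36: 9.3 points, p=0.32 |

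The arm-opposed result is still significant at 10 missing per arm and is lost at 11 (11/75 = 14.7%).

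**Odds-ratio scale.** The two planned runs are close but not identical. The crude odds ratios are 0.230 and 0.247 at 5 missing per arm, and 0.243 and 0.282 at 11. The arm-opposed value at 11 is 0.517.

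**Assumed weaker effect, 0.40 versus 0.60, 5 missing per arm.** The planned runs are 28 vs 42 and 33 vs 47, each 18.7 points with p=0.033. The arm-opposed run is 33 vs 42, 12.0 points, p=0.19.

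**Unequal missingness, design rates, 15 NexoBrid and 4 SOC missing.** The planned runs are 14 vs 43 (38.7 points) and 29 vs 47 (24.0 points). The arm-opposed run is 29 vs 43 (18.7 points). Here the all-excised run does move against NexoBrid, though not all the way.

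**The case against.** The strongest reply is that the plan expects few missing values. Section 11 anticipates that primary and secondary endpoint data will be available for all patients at the first analysis, apart from early drop-outs. At the design effect, about 15% would have to be missing per arm before the arm-opposed run overturned significance. That stands, and it keeps the point minor. The flip at 5 missing per arm relies on an effect weaker than the SAP anticipates (20 points against 36).

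It can also be said that excision is analysed on the odds-ratio scale, where the two runs are not identical, and that with unequal missingness they can differ materially. If data were missing only in the NexoBrid arm, the all-excised run would itself be the worst case. Both statements are correct. The exact coincidence holds for the risk difference with equal missing shares; the odds ratios are merely similar.

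A reader might extend the criticism to the primary endpoint, because its first two sensitivity analyses are the same kind of uniform fill. Section 10.1.1 does not support that. Its third analysis moves one arm only: "For the NexoBrid group the event probability will be" the observed rate less a shift that grows for as long as the result is non-negative. An assumption unfavourable to NexoBrid is therefore tested there.

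A reader might conversely take the opening reference in section 10.1.1.1 to carry the tipping-point analysis over to excision. The narrowing to the complete-case main analysis, and the count of two runs against three for the primary endpoint, rule this out.

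**Conclusion.** The point holds for surgical excision only. The two runs in section 10.1.1.1 fill both arms alike, do not bracket the possible results when missingness is similar, and leave untested the case unfavourable to NexoBrid. No tipping-point analysis makes up for this.

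The size depends on how much is missing, which the SAP does not state. At design rates the gap between the planned and arm-opposed results is 6.7 points at 5 missing per arm (33.3 − 26.7). At 11 per arm it reaches 14.7 points (30.7 − 16.0), where the arm-opposed run is no longer significant while both planned runs stay below p=0.001. With a weaker observed effect, far less missing data suffices.

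A reader might infer that the excision result is not robust. The documents do not support that: at the anticipated effect and modest missingness, the arm-opposed run would still favour NexoBrid. What fails is the ability of the planned runs to demonstrate robustness. The main analysis is unaffected. Minor severity; worth correcting because the remedy is cheap.

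**What to change.** In section 10.1.1.1, add a third sensitivity run that counts missing NexoBrid patients as excised and missing SOC patients as not excised. Alternatively, extend the tipping-point method of section 10.1.1 to excision, raising the imputed excision probability in the NexoBrid arm stepwise from its observed rate while holding SOC at its observed rate. Either run should report the odds ratio of section 11.1.3.1, with the number missing in each arm shown beside it.

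The cost is one extra analysis and a sensitivity result that may look less favourable. The primary endpoint needs no additional run on this account.

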10.1.1.2. Secondary Endpoint: Time to complete eschar removal

The analysis of the secondary endpoint time to eschar removal will compute missing values as censored at the date of the last non-missing eschar removal assessment (typically last debridement procedure).

